## 6.2 Handling of Missing Data and Outliers

### 6.2.1.1 Missing Menopause-Specific Quality of Life and Clinical Global Impression Data: For the MENQOL domains:

- If at least 50% of the items within a domain function score were answered (defined as at least 8 out of 16 questions are answered for physical domain, at least 4 out of 7 for psychosocial domain, and at least 2 out of 3 for vasomotor and sexual domains) the domain score will be calculated as the mean of the non-missing responses. For example: Vasomotor: if Q3 is missing (i.e. 2 items are not missing), then Score = (Q1+Q2)/2.
- If >50% of the items within a domain function score are missing, then the domain score will be considered as missing.

#### For the MENQOL total score:

- If at least 50% (at least 2 out of 4 domains) have non-missing scores, then the MENQOL total score will be calculated as the mean of the non-missing domains.
- If >50% (3 or 4 domains) are missing, then total score will be considered as missing.

#### For the CGI:

- missing data will not be imputed.

### 6.2.1.2 Handling of Missing or Incomplete Dates

Imputation rules for missing or partial AE Start Date are defined below.

#### If only day of AE Start Date is missing:

If the AE start year and month are the same as that for the Treatment Start Date, then:

- If the full (or partial) AE Stop Date is not before the Treatment Start Date or AE Stop Date is missing, then impute the partial AE start day as the day of Treatment Start Date;
- Otherwise, impute the partial AE start day as 1.

#### If day and month of AE Start Date are missing:

If AE start year = year of Treatment Start Date, then:

- If the full (or partial) AE Stop Date is not before the Treatment Start Date or AE Stop Date is missing, then impute the partial AE start month and day as the month and day of Treatment Start Date;
- Otherwise, impute the partial AE start month as January and the day as 1.

#### If Year of AE Start Date is missing:

If the year of AE start is missing or AE Start Date is completely missing, then:

- No imputation will be done.

If the year of AE start is missing and AE Stop Date is not missing, then:

---

- If the AE Stop Date is before the Treatment Start Date then the AE should be considered as a pre-treatment AE.
- Otherwise, the AE will be considered as TEAE.

Imputation rules for missing or partial medication start/stop dates are defined below:

**Missing or partial medication start date:**

- If only day is missing, use the first day of the month.
- If day and month are both missing, use the first day of the year.
- If day, month and year are all missing, use the date of informed consent.

**Missing or partial medication stop date:**

- If only day is missing, use the last day of the month.
- If day and month are both missing, use the last day of the year.
- If day, month and year are all missing, assign ‘continuing’ status to stop date.

### 6.3 COVID-19 Impact

The impact of COVID-19 will be continuously monitored during the study. At the time of writing the SAP, there is no relevant impact in term of screening failures, missing data and safety concern. If the impact becomes relevant in the future, post-hoc analysis may be performed.

## 7 STATISTICAL METHODS

### 7.1 General Statistical Conventions

All statistical procedures will be completed using SAS version 9.4 or higher, there is only one treatment group, thus no formal statistical analysis will be performed.

Confidence intervals (CIs) will be presented as 2-sided 95% CIs unless specified differently in specific analysis.

Categorical variables will be summarized using frequency counts (n) and percentages in each category, percentages will be computed for subjects with non-missing value (as the denominator). If there are missing values, missing values counts will be provided. All percentages will be rounded to one digit after decimal point. The frequency counts and percentages will be presented in the form XX (XX.X %), where the percentage is in the parentheses. If the percentage of a category is '100 %', then it will be displayed as '100 %' (no decimals will be added after 100).

Continuous variables will be summarized using the number of subjects with non-missing values (n), mean, median, standard deviation (SD), minimum (min), maximum (max) and missing values counts. Missing values counts will be displayed only if there are missing values. All mean and median values will be formatted to one more decimal place than the measured value. Standard deviations will be formatted to two more decimal places than the measured value. The min and max will be displayed to the same number of decimal places as the measured value. Unscheduled visits will not be summarized in tables.

Analyses will be performed by visit, irrespective of any time window deviations, unless otherwise specified. The early discontinuation (ED) visit will be separated from the scheduled EoT- visit based on discontinuation reason. Unscheduled visits related to efficacy data will be clustered with scheduled visits based on the visit windows in [Table 5](#) of Appendix 1. Similarly, the unscheduled visit results will be clustered with scheduled visits based on the visit windows defined in [Table 6](#) (Appendix 1) for microscopic findings and laboratory endpoints and endometrial biopsy. Similarly, the scheduled visits for ECG, Procedures, Questionnaire, Vital Signs, Imaging and Findings will be based on visit window [Table 7](#) in Appendix 1.

All subject data, including unscheduled data, will be presented in individual subject data listings. Unless otherwise stated, unscheduled visit results will be included in date/time chronological order, within listings. The subject's age will be stated on each listing. Unless specified, no imputed dates or values will be presented in listings.

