10.4.10. Endometrial Safety Assessment and Stopping Rules

A baseline endometrial biopsy will be obtained for all the non-hysterectomized subjects during the Screening period. An end-of-treatment endometrial biopsy is planned at the EoT Visit (Visit

7 in the Efficacy study part and Visit 6 in the Safety Study part) providing that the subject has been treated with E4 for at least 12 weeks.

Endometrial thickness will be measured at screening, Visit 4, Visit 5, Visit 6 and Visit 7 (EoT) in the Efficacy Study part and at screening, Visit 3, Visit 4, Visit 5 and Visit 6 (EoT) in the Safety Study part and subjects will record daily the vaginal bleeding events. If after the first 4 weeks of treatment, subject presents with a bi-layer endometrial thickness >10 mm as assessed by TVUS and/or presents with persistent and/or recurrent bleeding, confirmed by the investigator, an endometrial biopsy will be performed. If the biopsy shows disordered proliferative endometrium, hyperplasia or worse, the study drug will be discontinued, and the subject will be withdrawn from the study. The subject will be treated with P4 200 mg once daily for 14 days. At approximately 10-14 days after completion of the progestin treatment, a new TVUS will be performed to measure endometrial thickness and a biopsy will be carried out if deemed necessary by the Investigator to demonstrate the resolution. If the endometrial event has not resolved, treatment will be started according to local practice/guidelines. The pathologic diagnoses of DPE, hyperplasia and worse will be reported as AESI and the subject will be followed up until the resolution of the event. Resolution of disordered proliferative endometrium and hyperplasia should be documented by TVUS with endometrial thickness ≤4 mm or an endometrial biopsy repeated no earlier than 10-14 days after oral treatment with P4 200 mg/day for 14 days given after discontinuation of the subject.

Information on the treatment (including surgical treatment) and any additional pathology results will be reported.

Endometrial safety will be monitored during the trial by a DSMB (see Section 10.5).

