**Table 1: Derived Variables**

Variables	Formula																								
Demographic and Baseline Characteristics																									
Body mass index (BMI) (kg/m  )	weight (kg)/[height (m)] 																								
Study Treatment																									
Treatment Start Date	The date of first dose of study drug.																								
Treatment Stop Date	The date of last dose of study drug.																								
Duration of exposure (Days)	(Treatment Stop Date – Treatment Start Date) + 1																								
Treatment compliance (%)	100 x [(total number of tablets dispensed) – (total number of tablets returned)]/(duration of exposure in days)																								
Study Day	Prior to Treatment Start Date: Date of interest – Treatment Start Date  On or after Treatment Start Date: Date of interest – Treatment Start Date + 1																								
Study Week	
Study Week is defined as follows for the first 7 weeks
 
  
 Week	Start (Study Day)	End (Study Day)	
   
 1	1	7	
 
 2	8	14	
 
 3	15	21	
 
 4	22	28	
 
 5	29	35	
 
 6	36	42	
 
 7	43	49	
  
	Week	Start (Study Day)	End (Study Day)	1	1	7	2	8	14	3	15	21	4	22	28	5	29	35	6	36	42	7	43	49
Week	Start (Study Day)	End (Study Day)																							
1	1	7																							
2	8	14																							
3	15	21																							
4	22	28																							
5	29	35																							
6	36	42																							
7	43	49																							

Study Cycle	28-day period starting from Treatment Start Day
Adverse Events	
Adverse Event (AE) Start Day	Prior to Treatment Start Date: AE start date – Treatment Start Date  On or after Treatment Start Date: AE Start Date – Treatment Start Date + 1
AE Stop Day	Prior to Treatment Start Date: AE stop date – Treatment Start Date  On or after Treatment Start Date: AE stop date – Treatment Start Date + 1
AE Duration (Days)	(AE Stop Date – AE Start Date) + 1

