### 7.7.1.12.2 Analysis of Endometrial Tissue

All the analyses of endometrial tissues will be performed only for non-hysterectomized subjects.

- Initial diagnosis (from first safety reader, based on adequate samples only)
  - By visit analysis: The Initial diagnosis will be summarized at each visit.
- Safety diagnosis
  - By visit analysis: The Safety diagnosis will be summarized at each visit.
- Final/Consensus diagnosis
  - By visit analysis: The Final/Consensus diagnosis will be summarized at each visit performed on-treatment.
  - Worst case analysis across all visits: The worst case derived from all on-treatment visits, including unscheduled visits, will be summarized for Final/Consensus diagnosis.

Visits will be clustered as specified in [Table 6](#) of Appendix 1.

Frequency counts (n), percentages and the 95% CIs of the histologic characteristics of the endometrium including no tissue, tissue insufficient for diagnosis, atrophic, inactive, proliferative - weakly proliferative, proliferative - active proliferative, proliferative - disordered proliferative, secretory - cyclic type, secretory - progestational type (including stromal decidualization), menstrual type, simple hyperplasia without atypia, simple hyperplasia with atypia, complex hyperplasia without atypia, complex hyperplasia with atypia, carcinoma for Initial diagnosis and Safety diagnosis will be summarized separately by visits for the Safety Analysis Set.

Frequency counts (n), percentages and the 95% CIs of the additional pathological results including polyps, stromal tissue, metaplasia and cervical tissue for Safety diagnosis will be summarized separately by visits for the Safety Analysis Set.

Frequency counts (n), percentages and the 95% CIs of benign endometrium (including subcategory 1a with disordered proliferative as consensus diagnosis), simple hyperplasia without atypia, complex hyperplasia without atypia, simple hyperplasia with atypia, complex hyperplasia with atypia (including total for all hyperplasia), carcinoma will be summarized separately by visits for the Safety Analysis Set for Final/Consensus diagnosis. Worst-case analysis across all on-treatment visits will also be summarized for the Safety Analysis Set for the Final/Consensus diagnosis.

A listing will be provided of all subjects with all biopsy results from each pathologist, and the Initial, Safety diagnosis and Final/Consensus diagnosis for the Included Set.

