#### **7.7.1.13 Vaginal Bleeding and/or Spotting**

Absence or occurrence of vaginal bleeding and/or spotting on a daily basis will be assessed using the scale below:

- 0 = Absence of vaginal bleeding or spotting;
- 1 = Spotting: evidence of minimal blood loss requiring none or at most one pad, tampon or panty liner per day;
- 2 = Bleeding: evidence of blood loss requiring more than one pad, tampon or panty liner per day.

Frequency counts (n) and percentage of subjects with absence of any bleeding and/or spotting during the cycle, with vaginal bleeding and/or spotting during the cycle, with bleeding only during the cycle, with spotting only during the cycle will be provided for each 28- day cycle of treatment based on data in the subject diary (in non-hysterectomized subjects) for the Safety Analysis Set.

The number of days with bleeding or spotting, as reported on subject diaries, will be summarized by 28-day cycle of treatment.

A listing will be provided for vaginal bleeding and/or spotting and/or amenorrhea for the Included Set.

The following data will be excluded from analysis of endpoints for bleeding (to be analysed separately)

- bleeding for the day on which an endometrial biopsy was performed and 6 days after biopsy and
- bleeding reported after discontinuation of study drug (for example withdrawal bleeding, on P4 treatment)

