**Table 6: Visit Window Microscopic Findings and for Laboratory Endpoints**

Assessment Visit	Time window	Visit
Safety Visit 2		Week 5
Safety Visit 3		Week 13
Safety Visit 4		Week 29
Safety Visit 5		Week 41
Safety Visit 6/EoT		Week 53 (if discontinuation reason is missing in DS domain) Early Discontinuation (if discontinuation reason is non-missing in DS domain)
Safety Visit 7 Follow-up		Week 55/56 Follow-up
Unscheduled Visits	<0, 2 to 18	Unscheduled
	1	Visit 1 Baseline
	19 to 46	Week 5
	47 to 74	Week 9
	75 to 144	Week 13

	145 to 242	Week 29
	243 to 325	Week 41
	326 to 375*	Week 53
	>=327#	Week 53
	>=376*	Week 55/56 Follow-up

Note: \*only for non-hysterectomized subjects; #: only for hysterectomized subjects

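### SAP Table 6 places unscheduled biopsies by study day alone, so a post-progesterone resolution biopsy can be tabulated as a treatment-week result

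*SAP*

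**What the plan says.** **Windowing.** SAP 7.1 says that "the unscheduled visit results will be clustered with scheduled visits based on the visit windows defined in" Table 6 for laboratory endpoints, microscopic findings and endometrial biopsy. In Table 6 the unscheduled windows are ranges of study day. SAP Table 1 computes study day, from the first dose onward, as "Date of interest – Treatment Start Date + 1". Neither table refers to the last E4 dose or to P4. Table 6 also has a nominal row, "Safety Visit 7 Follow-up", with no day range.

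**A competing sentence.** SAP 7.1 also says: "Unscheduled visits will not be summarized in tables".

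**Which tables use the windows.** SAP 7.7.1.12.2 clusters biopsy visits by Table 6.
- Safety diagnosis: "The Safety diagnosis will be summarized at each visit". The Initial diagnosis is treated the same way. Neither has an on-treatment limit.
- Final/Consensus diagnosis: the by-visit summary is restricted to visits on treatment. For the worst case, "The worst case derived from all on-treatment visits, including unscheduled visits, will be summarized for Final/Consensus diagnosis". SAP 7.7.1.12.1 makes this the diagnosis used for the endometrial endpoint.

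**The biopsy in question.** Protocol 10.4.10 covers a woman whose biopsy shows disordered proliferative endometrium, hyperplasia or worse. E4 is stopped and P4 is given for 14 days. About 10–14 days after that, "a new TVUS will be performed to measure endometrial thickness and a biopsy will be carried out if deemed necessary by the Investigator". The procedures listed for Visit 7 (Protocol 10.1.6.7) include TVUS but no biopsy.

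**Off-drug rules elsewhere.** SAP 7.7.1.13 removes "bleeding reported after discontinuation of study drug" from the bleeding endpoints and gives the P4 period as an example. SAP 7.7.1.2 stops laboratory summaries 30 days after the last dose. No such rule is stated for biopsies.

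**The concern.** The endometrial tables are meant to describe histology under unopposed E4. A resolution biopsy is taken after E4 has stopped and after a progestin course intended to reverse the finding. If it carries a treatment-week label, the row mixes two different exposures. A resolved sample makes that week look more benign. A persisting lesion appears as a treatment-week finding in a woman no longer on E4.

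The rows at risk are thin. No biopsy is scheduled between screening and EoT, so the Week 5 to Week 41 rows hold only for-cause samples and a few misplaced ones would show. The SAP also gives no rule for choosing between two biopsies from one woman in the same window. Early stopping is expected to be common: Protocol 8.1 anticipates 50% drop-out by 12 months in the Safety Study part, although only some of it would be for endometrial findings.

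**Working it through.** The plan states no figure to reproduce. The check is day arithmetic against Table 6.

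**Inputs**
- Table 6, unscheduled records, non-hysterectomized women: Days 19–46 Week 5; 47–74 Week 9; 75–144 Week 13; 145–242 Week 29; 243–325 Week 41; 326–375 Week 53; 376 onward Follow-up.
- P4 course 14 days, then about 10–14 days to the resolution check (Protocol 10.4.10).
- Scheduled TVUS, one of the two biopsy triggers: Visit 3 Days 85–91, Visit 4 Days 197–203, Visit 5 Days 281–287, Visit 6 Days 365–371 (SAP Table 5).
- Assumption: P4 starts the day after the last E4 dose. A later start lengthens the gap.
- Assumption: L, the time from the positive biopsy to the last E4 dose, is 0–28 days. The documents do not give it.

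**Step 1. Gap from last E4 dose to resolution biopsy.** 14 + 10 = 24 days to 14 + 14 = 28 days, or more.

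**Step 2. Label by day of last E4 dose** (window limits minus the gap).

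| Label if entered as unscheduled | Last dose, 24-day gap | Last dose, 28-day gap |
|---|---|---|
| Week 13 | Day 51–120 | Day 47–116 |
| Week 29 | Day 121–218 | Day 117–214 |
| Week 41 | Day 219–301 | Day 215–297 |
| Week 53 | Day 302–351 | Day 298–347 |
| Follow-up | Day 352 or later | Day 348 or later |

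Stopping earlier than the first row puts the sample in Week 9, a row with no matching Safety-part visit.

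**Step 3. Example.** Last E4 dose Day 130; P4 Days 131–144; biopsy Day 156, which is 12 days after P4 and 26 days after E4. Day 156 lies in 145–242, so the label is Week 29.

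**Step 4. Label by day of the positive biopsy.** Resolution day = biopsy day + L + 24 to 28.

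| Positive biopsy at | L = 0 | L = 14 | L = 28 |
|---|---|---|---|
| Visit 3 | Day 109–119, Week 13 | Day 123–133, Week 13 | Day 137–147, Week 13 or 29 |
| Visit 4 | Day 221–231, Week 29 | Day 235–245, Week 29 or 41 | Day 249–259, Week 41 |
| Visit 5 | Day 305–315, Week 41 | Day 319–329, Week 41 or 53 | Day 333–343, Week 53 |
| Visit 6 | Day 389–399, Follow-up | Day 403–413, Follow-up | Day 417–427, Follow-up |

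For L up to 7 days at Visits 3, 4 and 5, the resolution biopsy falls in the same row as the positive biopsy it follows. With a longer L it can move to the next row. Women stopped at the scheduled end of treatment are labelled correctly.

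**Step 5. Which tables take it.** For the Initial and Safety by-visit tables, no on-treatment condition removes a sample clustered under Table 6. For Final/Consensus, entry depends on the meaning of on-treatment. SAP 3.1 uses the term for Visits 2–6, and nothing ties it to dosing. Read from the Table 6 week label, it admits these samples; read in the ordinary sense, it excludes them.

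**Step 6. Borrowing the laboratory rule.** A cut-off 30 days after the last dose would not exclude samples taken at 24–28 days.

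**The case against.** The strongest reply is that these samples may never reach a treatment-week row.

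- Visit 7 also takes place after early discontinuation, about 10 days after P4 ends, which is close to the time of the resolution check. A biopsy entered there keeps the Follow-up label whatever its study day. This stands. The misplacement applies only to records entered as unscheduled, and the documents do not say which form sites use.
- The biopsy is discretionary, and Protocol 10.4.10 allows resolution to be documented by TVUS instead. The documents also do not say that resolution biopsies go through the central readers who supply these tables. Both points stand and leave the frequency unknown.
- The endpoint-serving Final/Consensus tables are already limited to on-treatment visits. This stands in part: the limit exists, but it is undefined.
- SAP 7.1 also keeps unscheduled visits out of tables. That contradicts the clustering rule and the worst-case rule, which both bring them in, so it adds an ambiguity and does not settle the matter.
- The analysis is single-arm and descriptive, and every biopsy is listed by reader. This limits the harm, but the tables should still be right.

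A reader might infer that the endometrial event rate is diluted by a calculable amount. With assumed counts, 4 positives in 8 for-cause biopsies (50%) would become 4/12 (33%) after adding 4 benign resolution biopsies. The documents do not support that figure. It requires counting biopsies and not women, whereas the endpoint is a frequency of subjects, SAP 7.1 uses subjects as denominator, and SAP 7.7.1.12 refers to evaluable biopsies.

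**Conclusion.** The defect is real but narrow. Table 6 assigns biopsies recorded as unscheduled to treatment-week rows with no reference to the last E4 dose or P4. A post-P4 resolution biopsy in a woman who stopped before about Day 348–352 would then carry a treatment-week label, and no on-treatment limit keeps it out of the Initial and Safety by-visit tables. The Final/Consensus by-visit and worst-case tables are exposed only if on-treatment is read from the week label.

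Three stronger readings are tempting and not supported. The first is that all such biopsies will be tabulated as treatment weeks: Visit 7 entries are not, and SAP 7.1 contradicts itself on unscheduled visits. The second is that the endpoint result is plainly contaminated: its tables carry an on-treatment limit. The third is that the worst-case rate is lowered: a benign later sample cannot displace a worse earlier one.

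The day limits rest on P4 starting directly after E4 and on the 10–14 day interval being kept. The number of women affected cannot be computed from the documents. The correction should be made before the tables are programmed, because a stated rule yields a wrong label and the remedy is cheap.

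**What to change.** Amend SAP 7.1, Table 6 and 7.7.1.12.2 as follows.

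1. Define an on-treatment biopsy as one taken before the first dose of P4 or another progestin and no later than the EoT/early-discontinuation visit. A strict last-dose cut-off would not serve: Protocol 10.1.6.6 puts the last dose on the evening before the EoT visit, so the scheduled EoT biopsy would be lost.
2. Apply this definition to the Initial, Safety and Final/Consensus by-visit tables and to the worst-case table.
3. Tabulate every later biopsy in a separate post-treatment follow-up row, whether entered under Visit 7 or as unscheduled.
4. State that the worst on-treatment result per woman per window is used, with women as the denominator.
5. Reconcile the sentence that keeps unscheduled visits out of tables with the Table 6 clustering rule.

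The cost is one derivation from dates already collected and one extra table row. No clinical procedure changes.
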